6.2 IMPORTANT PROTOCOL DEVIATIONS

Data discrepancies and deviations from the CTP will be identified for all patients in the database (i.e., enrolled patients). Consistency check listings (for identification of deviations of time windows) and a list of protocol deviations will be provided to be discussed at the RPM/DBLM. At this meeting, it will be decided whether a discrepant data value can be used in analyses or whether it must be queried in the clinical database. Each protocol deviation must be assessed to determine whether it is an important Protocol Deviation (iPD). The categories of iPD are defined in the Integrated Quality and Risk Management plan (IQRMP). These categories are repeated below in order to ensure that those iPD which lead to exclusion from the PPS are suitably documented before unblinding and locking of data.

For definition of iPDs, and for the process of identification of these, refer to the BI reference document "Identify and Manage Important Protocol Deviations (iPD)" [\(2\)](#).

If any patients fulfil the iPD categories, then they are to be summarized and will be captured in the RPM/DBLM minutes via an accompanying Excel spreadsheet [\(3\)](#). The following table contains the categories which are considered to be iPDs in this trial. If the data show other iPDs, for example, based on monitor visits to the site(s), then this table will be supplemented accordingly by the time of the RPM/DBLM. Not all iPDs will lead to exclusion from analysis sets. iPDs leading to exclusion from analysis sets are indicated as such in [Table 6.2: 1](#).

iPDs will be summarized and listed for the randomized set.

Table 6.2: 1 Important protocol deviations

Category / Code	Description	Comments	Excluded from
A	Entrance criteria violated		
A1	Inclusion criteria not met		
A1.01	GPP per CTP not confirmed	Inclusion criterion 1	PPS#
A1.02	Retinoids/methotrexate/cyclosporine not discontinued prior to first dose of study treatment	Inclusion criterion 2	PPS
A1.03	Age out of range	Inclusion criterion 3 Also programmatic check required	None
A1.04	Women of childbearing potential not to agree to use effective method of birth control;	Inclusion criterion 5	None
A2	Exclusion criteria violated		
A2.01	SAPHO syndrome	Exclusion criterion 1	PPS
A2.02	Primary erythrodermic psoriasis vulgaris	Exclusion criterion 2	PPS
A2.03	Primary plaque psoriasis vulgaris without presence of pustules or with pustules that are restricted to psoriatic plaques	Exclusion criterion 3	PPS
A2.04	Drug-triggered Acute Generalized Exanthematous Pustulosis (AGEP)	Exclusion criterion 4	PPS
A2.05	Immediate life-threatening flare of GPP or requiring intensive care treatment	Exclusion criterion 5	PPS
A2.06	Severe, progressive, or uncontrolled hepatic disease	Exclusion criterion 6	None
A2.07a	Any restricted medication, or any drug, with potential influence on safe conduct of study	Exclusion criterion 7	PPS#
A2.07b	Any prior exposure to Spesolimab or another IL36R inhibitor	Exclusion criterion 7	PPS#
A2.08	Dose escalation of cyclosporine and/or methotrexate and/or retinoids within the 2 weeks prior to first study treatment	Exclusion criterion 8 Also programmatic check required	PPS#
A2.09	The initiation of systemic agents 2 weeks prior to first study treatment	Exclusion criterion 9 Also programmatic check required	PPS#

Table 6.2: 1 Important protocol deviations (cont'd.)

Category / Code	Description	Comments	Excluded from
A2.10	Congestive heart disease	Exclusion criterion 10	None
A2.11	Active systemic infections during the last 2 weeks prior to first study treatment	Exclusion criterion 11	None
A2.12	Increased risk of infectious complications	Exclusion criterion 12	None
A2.13	Relevant chronic or acute infections including HIV or viral hepatitis.	Exclusion criterion 13	None
A2.14	Active or Latent TB	Exclusion criterion 14	None
A2.15	History of allergy/hypersensitivity to a systemically administered trial medication agent or its excipients	Exclusion criterion 15	None
A2.16	Any documented active or suspected malignancy or history of malignancy within 5 years prior to screening	Exclusion criterion 16	None
A2.17	Currently enrolled or less than 30 days since another investigational device or drug study	Exclusion criterion 17	PPS
A2.18	Pregnancy	Exclusion criterion 18	None
A2.19	Major surgery within 12 weeks prior to first study treatment	Exclusion criterion 19	None
A2.20	Clinical Evidence which would make the study participant unreliable to adhere to the protocol	Exclusion criterion 20	PPS
B			
Informed consent			
B1	Informed consent not available	Inclusion criterion 4; Date of informed consent missing or no signature on patient's "Declaration of Informed Consent" In this case: Patient's data will not be used at all.	All#
B2	Informed consent too late	Informed consent date was after Visit 1	None

Table 6.2: 1 Important protocol deviations (cont'd.)

Category / Code	Description	Comments	Excluded from
C	Trial medication and randomization		
C1	Incorrect trial medication		
C1.01	Missing medication or incorrect medication received by patients due to other reasons	At least one randomized vial was given wrongly or missing at Day 1 due to other reason.	PPS
C1.02	Missing medication or incorrect medication received by patients due to COVID-19	Can only be finally judged after DBL since unblinding information is required	At least one randomized vial was given wrongly or missing at Day 1 due to COVID-19.
			PPS
C2	Non-compliance		
C2.01	Non-compliance with study drug intake- - administered dose too low or too high	Study medication dose (based on infusion volume) is less than 80% or more than 120% of the total planned dose	PPS
C3	Randomization not followed		
C3.01	Treated without randomisation	Patient treated according to eCRF, but not randomised according to IVRS.	PPS/RS/SAF
C3.02	Randomization order not followed	Stratification error Programming check and also manual review after DBL	None#
C4	Medication code broken		
C4.01	Medication code broken inappropriately	Medication code was broken prior to the DBL for no valid reason.	PPS#
		Final decision at the DBL meeting based on medical judgment.	

Table 6.2: 1 Important protocol deviations (cont'd.)

Category / Code	Description	Comments	Excluded from
D	Concomitant medication		
D1	Previous medication		
D1.01	Washout of previous medication too short	Washout period too short - See Table 4.2.2.1: 1 in CTP	PPS#
D2	Prohibited medication use		
D2.01a	Use of prohibited med (with potential influence on eff. data) when not provided as an escape treatment to stabilize a worsening disease condition – prior to or up to Week 1	See the list of restricted medication in CTP, Table 4.2.2.1: 1, manual assessment at MQRM/RPM/DBLM	PPS#
D2.01b	Use of prohibited med (with potential influence on eff. data) when not provided as an escape treatment to stabilize a worsening disease condition – after Week 1	See the list of restricted medication in CTP, Table 4.2.2.1: 1, manual assessment at MQRM/RPM/DBLM	None#
D2.01c	Use of prohibited med (without potential influence on eff. data)	See the list of restricted medication in CTP, Table 4.2.2.1: 1, manual assessment at MQRM/RPM/DBLM	None#
D3	Change in Background medication		
D3.01	Background medication (methotrexate, cyclosporine, or retinoids) not stopped prior to receiving first study treatment on Day 1	Background medication continues into the treatment period	PPS#
E	Missing data		
F	Study specific analysis		
F1	Other trial specific deviation		
F1.01	Study drug intake outside time window	Infusion period takes longer than 180 minutes.	None
F1.02	Patient was administered open-label treatment at Day 8 with Spesolimab but did not qualify for this treatment per CTP requirement.	Patient was Spesolimab retreated but did not show a GPPGA of ≥ 2 and a pustular sub-score ≥ 2 at Day 8	None
F1.03	Patient was administered rescue treatment with Spesolimab but did not achieve flare qualification per CTP requirement.	Flare qualification requires: ≥ 2 point increase in GPPGA score & pustulation subscore of GPPGA ≥ 2 after achieving a clinical response (GPPGA 0 or 1)	None#

Table 6.2: 1 Important protocol deviations (cont'd.)

Category / Code	Description	Comments	Excluded from
G Other safety related deviations			
G1	Pregnancy test not done for woman of child bearing potential at days of IMP treatment and not prior the IMP administration	Pregnancy test not done before randomized treatment at Day 1, OL Spesolimab at Day 8 or rescue Spesolimab	None#

PD will be detected manually;

Source: BI reference document ' Identify and Manage Important Protocol Deviations (iPD)' [001-MCS-50-413] (2, 12).

6.3 PATIENT SETS ANALYZED

The following analysis sets will be defined for this trial:

- **Enrolled Set (ES):**
This patient set includes all patients who signed informed consent. It will be used for analyses of patient disposition.
- **Randomized Set (RS):**
This patient set includes all randomized patients. Treatment assignment will be as randomized. It will be used for analyses of patient baseline demographics and disease characteristics, and is the main set for the analyses of efficacy endpoints.
- **Safety Analysis Set (SAF):**
This patient set includes all patients who were randomized and received at least one dose of study drug on Day 1. This is the main analysis set for safety. Patients will be analyzed according to the actual treatment received.
- **Per-Protocol Set (PPS):**
This patient set includes all patients in the randomized set who adhered to the CTP without any iPDS which are flagged for exclusion from the PPS in the table above. The PPS will be used for sensitivity analysis on the primary and key secondary endpoints.

The discussion of all exceptional cases and problems and the decisions on the allocation of patients to populations will be made at latest at the RPM/DBLM.

Handling of Treatment Misallocations in Analysis Sets

If a patient is randomized but not treated, they will be reported under their randomized treatment group for efficacy analysis according to RS and PPS (per the intent-to-treatment principle). By definition, however, such patients are excluded from the safety analyses since no randomized study medication was taken.

If a subject is treated but not randomized, they will be excluded from the efficacy analysis and safety analysis by definition. However, subjects under such circumstances will be described in the final clinical trial report.

If a subject is randomized but took incorrect treatment during the study, then:

- For efficacy analyses according to the RS and PPS, they will be reported under their randomized treatment group.
- For safety analyses using the SAF which are based on actual treatment:
 - If a subject is planned to receive a single dose administration of Spesolimab (randomized to 900 mg SD), then they will be reported under the Spesolimab 900 mg SD group if the subject receives at least 1 vial of randomized Spesolimab on Day

1. A subject will be assigned to the placebo treatment group only if they are treated and receive no vials of randomized Spesolimab on Day 1.
- If a subject is planned to receive placebo treatment, then they will be reported under the placebo arm if they are treated and receive no vial of randomized Spesolimab on Day 1. If the subject receives ≥ 1 vial of randomized Spesolimab on Day 1, then the patient will be reported as treated with Spesolimab 900 mg SD treatment group.

[Table 6.3: 1](#) illustrates the data sets which are to be used for each category class of endpoints, and the approaches used with regard to missing data including estimand concepts.

Table 6.3: 1 Overview of use of patient analysis sets by class of endpoint and handling of estimand and missing data

Class of endpoint	ES	SAF	RS	PPS
Disposition	OR		OR	
Compliance and exposure		OR		
iPD			OR	
Demographic/baseline characteristics			OR	
Concomitant medication			OR	
Primary endpoint and key secondary endpoint			EN-NRI, EN-NRI ¹ EN-BRI ¹ , EN-EM ¹ EN-PC-NRI ¹ OC ² , OC-IR ²	EN-NRI ¹ ,
Secondary binary efficacy endpoints			EN-NRI, EN-NRI ¹³ EN-BRI ¹³ OC ² , OC-IR ²	
Secondary continuous efficacy endpoints			EN-LOCF, EN-LOCF ¹³ EC-MMRM ¹ , EC-LOCF ¹ OC ² , OC-IR ²	
Safety data		OR OC-IE OC-IR ¹		

¹ sensitivity/further analysis or subgroup analysis

² descriptive display only

³ for secondary endpoints included in the testing strategy only

For explanation of the different approaches with regard to missing data see [Section 6.6](#).

EN: Primary estimand for binary and continuous endpoints. Death or any use of escape medication, or OL Spesolimab use at D8, or rescue medication with Spesolimab, prior to observing the endpoint(s) is considered to represent a non-response in the analysis of this endpoint outcome.

EN-PC: Alternative estimand for binary endpoints. Death or any use of escape medication, or OL Spesolimab use at D8, or rescue medication with Spesolimab, prior to observing the endpoint(s) is considered to represent a non-response in the analysis of this endpoint outcome. Any data after the use of restricted medication for other purpose will be censored.

EN-ID8: Alternative estimand for binary and continuous endpoints. Death or any use of escape medication, or rescue medication with Spesolimab, prior to observing the endpoint(s) is considered to represent a non-response in the analysis of this endpoint outcome.

[figure not shown]
EC: Alternative estimand for continuous endpoint. Any data post escape medication use or OL Spesolimab use at D8, or rescue medication with OL Spesolimab will be censored.

[figure not shown]
EC-ID8: Alternative estimand for continuous endpoint. Any data post escape medication use or rescue medication with OL Spesolimab will be censored.

NRI, BRI, EM, LOCF and MMRM represent analyses involving imputed data, cf. [Section 6.6.2](#).

OC = observed cases excluding values after any use of escape medication, or OL Spesolimab use at D8, or rescue medication with Spesolimab, OC-IR = observed cases including also values after any use of escape medication, or OL Spesolimab use at D8, or rescue medication with Spesolimab, OC-IE = observed cases excluding values after any use of OL Spesolimab use at D8, or any rescue medication with Spesolimab, OC-ID8 = observed cases excluding values after any use of escape medication, or rescue medication with Spesolimab.

OR = original results.

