7.3 PLANNED ANALYSES

The primary analysis of this trial is planned to be performed once all randomized patients have completed the 12 week period or early discontinued from the trial; a database lock for the primary analysis will then be performed. Final analysis is planned to be performed at the end of the trial once all randomized patients have completed the trial (including any follow-up period) if applicable.

The primary analysis and final analysis may be performed as a single analysis (at the time of trial completion), if, prior to the time of the primary analysis, the trial team agrees that the expected time interval between the planned analyses is insufficient to justify the performance of separate analyses.

Details of treatment unblinding for the primary analysis and final analysis are described in [Section 4.1.5.1](#). Details of the analysis to be performed will be described in the TSAP.

There will be 3 main patient populations in this trial for analyses: the randomized set (RS), the safety set (SS), and the per-protocol set (PPS).

Randomized Set

This patient set includes all randomized patients. Treatment assignment will be as randomized. This is the main analysis set for presentation of efficacy.

Safety Set

This patient set includes all patients who were randomized and received at least one dose of study drug. It will be the main analysis set for presentation of safety. Patients will be analyzed according to the actual treatment.

Per-Protocol Set

This patient set includes all patients in the RS who adhered to the CTP without any Important Protocol Violations (IPVs) potentially affecting the study outcome which lead to exclusion from the PPS. This set will be used for sensitivity analysis on the primary, key secondary, and secondary efficacy endpoints which are included in the testing hierarchy.

Important violations of the protocol will include violations of the key inclusion and exclusion criteria, incorrect medications taken, concomitant use of restricted medications, escape medication given without evidence for disease worsening, and any other violations of the protocol deemed important by the study team. All decisions concerning important protocol violations will be made prior to un-blinding of the database for the final trial analysis.

Further analysis sets, e.g. for the BM assessments, will be defined in the Trial Statistical Analysis Plan (TSAP).

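### SAP 6.3 places a randomized but untreated patient in the per-protocol set, while SAP Table 6.2: 1 and the set's own definition exclude that patient; the incorrect-treatment bullet is ambiguous in the same way

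*SAP*

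**What the plan says.** **Text that excludes.** SAP Table 6.2: 1 marks three medication deviations for exclusion from the PPS:
- C1.01: "At least one randomized vial was given wrongly or missing at Day 1 due to other reason".
- C1.02: "At least one randomized vial was given wrongly or missing at Day 1 due to COVID-19".
- C2.01: "Study medication dose (based on infusion volume) is less than 80% or more than 120% of the total planned dose".

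SAP 6.3 defines the PPS as the randomized patients who kept to the protocol "without any iPDS which are flagged for exclusion from the PPS in the table above". Protocol 7.3 points the same way: "Important violations of the protocol will include violations of the key inclusion and exclusion criteria, incorrect medications taken".

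**Text that keeps.** Under the misallocation heading in SAP 6.3, a patient who is randomized but not treated is covered by "they will be reported under their randomized treatment group for efficacy analysis according to RS and PPS", with the intention-to-treat principle given as the reason. For a patient who is randomized but takes incorrect treatment during the study, the efficacy bullet reads: "For efficacy analyses according to the RS and PPS, they will be reported under their randomized treatment group".

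**Role of the set.** SAP 6.3: "The PPS will be used for sensitivity analysis on the primary and key secondary endpoints". The RS is the main efficacy set. Neither document says which rule takes precedence.

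**The concern.** A per-protocol set is meant to show the effect in patients treated as planned. A patient who received no study drug is the clearest departure from that. Intention-to-treat is a reason for keeping such a patient in the RS, and it does not justify a place in the PPS. Two programmers working from SAP 6.3 could build different sets: one would apply the deviation flags, the other the misallocation text.

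What is at stake is a named sensitivity analysis of the primary and key secondary endpoints, in a trial that protocol 1.3 says will support first registration. With 17 placebo patients, one patient's membership is visible in the rates.

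**Working it through.** **1. The rules side by side**

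| Patient | Table 6.2: 1 and PPS definition | Misallocation text in 6.3 |
|---|---|---|
| Randomized, not treated | Out. Day 1 vials are missing (C1.01 or C1.02), and a dose of 0% is below 80% (C2.01, literal reading) | In, under the randomized arm |
| Wrong vial on Day 1, e.g. placebo patient given spesolimab | Out (C1.01 or C1.02) | In under the randomized arm, or merely labelled by that arm if otherwise in the set |
| Open-label Day 8 or rescue dose without qualifying (F1.02, F1.03) | Stays in (flagged None) | In, under the randomized arm |

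The first row is a direct conflict. The second is a conflict on one of two readings. The third is not a conflict.

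**2. Inputs.** 34 spesolimab and 17 placebo patients (protocol synopsis and 7.7). Suissa-Shuster Z-pooled test, one-sided 0.025 (protocol 7.3.1). Planned rates 0.6 and 0.1, endpoint correlation 0.65 (protocol 7.7). The documents give no number of untreated or wrongly treated patients; a range of 0 to 3 is assumed.

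**3. Check of the test against the plan's own figure.** With x1 responders of n1 on spesolimab and x2 of n2 on placebo, and pooled rate p = (x1 + x2)/(n1 + n2),

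Z = (x1/n1 − x2/n2) / √[p(1 − p)(1/n1 + 1/n2)].

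The p-value is the probability of a Z at least as large as that observed, maximised over the common response rate. At 0.6 against 0.1 with 34:17, exact power is 96.3% for the primary endpoint (stated 96.3%). Simulated joint power with both endpoints is 93.9% (stated 93.9%).

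**4. Size of keep against drop**
- Untreated spesolimab patient counted as a non-responder: 20/34 = 58.8% kept, 20/33 = 60.6% dropped; 1.8 points.
- Placebo patient given spesolimab who clears: 2/17 = 11.8% kept, 1/16 = 6.3% dropped; 5.5 points.

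**5. Effect on the PPS test, illustrative counts, one-sided exact p**

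| Situation | Kept | Dropped |
|---|---|---|
| Near plan, one untreated spesolimab non-responder | 20/34 vs 2/17, p = 0.0009 | 20/33 vs 2/17, p = 0.0007 |
| Near plan, one untreated placebo non-responder | 20/34 vs 2/17, p = 0.0009 | 20/34 vs 2/16, p = 0.0015 |
| Near plan, one placebo patient given spesolimab who clears | 20/34 vs 2/17, p = 0.0009 | 20/34 vs 1/16, p = 0.0004 |
| Borderline, one placebo patient given spesolimab who clears | 13/34 vs 2/17, p = 0.039 | 13/34 vs 1/16, p = 0.018 |
| Borderline, one untreated placebo non-responder | 14/34 vs 2/17, p = 0.0215 | 14/34 vs 2/16, p = 0.0355 |
| Borderline, three untreated spesolimab non-responders | 13/34 vs 2/17, p = 0.039 | 13/31 vs 2/17, p = 0.022 |

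Worked for the fourth row. Kept: p = 15/51 = 0.294 and Z = 0.265/0.135 = 1.96. Dropped: p = 14/50 = 0.280 and Z = 0.320/0.136 = 2.35.

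Near the planned rates no case changes significance. At borderline counts the choice of rule can change it, in either direction.

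**The case against.** **Membership is set in one place.** The PPS definition points to the table, and the misallocation text may only say under which arm a patient is reported. This has force for the incorrect-treatment bullet, which sits opposite a safety bullet based on actual treatment. So a reader might infer that the SAP plainly counts a placebo patient given spesolimab on Day 1 as a per-protocol placebo patient. The documents do not support that as a settled rule, because on the arm-label reading C1.01 has already removed the patient. The defence fails for untreated patients. They always have missing Day 1 vials and can never be in the PPS under the table, so the mention of the PPS in their sentence would have nothing to act on.

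**The bullet does other work.** It covers errors during the study, whereas C1.01 and C1.02 concern Day 1 only. Patients with F1.02 or F1.03 stay in the PPS, and the bullet gives their arm. This stands. Striking the PPS from both places looks free of cost, but it would remove that rule.

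**The decision is made blind.** One might infer that the conflict would be settled once the case and treatment are known. The documents do not go that far. SAP 6.2 has PPS-excluding categories documented before unblinding and lock, SAP 6.3 settles allocation to sets by the report planning or database lock meeting, and protocol 7.3 requires violation decisions before unblinding for the final analysis. A remark in the C1 rows of Table 6.2: 1 does say that final judgement must wait until after lock, because unblinding information is needed. It can be read as concerning whether a wrong vial was given, and it does not reopen the exclusion rule. It is still a reason to have a single rule beforehand.

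**Such patients should be rare.** Protocol 6.2.2 makes allocation and dosing the last activity at Visit 2, apart from post-dose checks. This is fair, and it limits the point.

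**Conclusion.** The contradiction is real for randomized but untreated patients and possible, on one reading, for a wrong vial on Day 1. Its reach is narrow. It affects only the PPS sensitivity analysis, and only if such a patient occurs.

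The size per patient is about 1.8 points for an untreated spesolimab non-responder and about 5.5 points for a placebo patient given spesolimab who clears. A reader might instead use one patient's weight, 1/34 = 2.9 or 1/17 = 5.9 points. That measures a changed outcome with the denominator fixed, whereas the question here is whether the patient is in the set at all.

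These figures assume response counts near the planned rates, and that an untreated patient is counted as a non-responder, as non-response imputation would do with no Week 1 assessment. The p-value crossings rest on counts chosen to be borderline. The documents give no ground for extending the point to the RS test, its alpha or its power. This is a minor correction to the SAP text.

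**What to change.** Before unblinding, make two edits to the misallocation text in SAP 6.3:

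1. In the sentence on randomized but untreated patients, delete *and PPS*, so that the randomized-arm rule there applies to the RS only.
2. In the efficacy bullet on incorrect treatment, limit the PPS wording to patients not excluded under C1.01, C1.02 or C2.01. Patients with later treatment errors who remain in the PPS are then still reported under the randomized arm.

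The cost is a small wording change. No analysis, table shell or sample size figure is affected, and the text then agrees with Table 6.2: 1, the PPS definition and protocol 7.3. If the sponsor does want untreated patients in the PPS, the entries in Table 6.2: 1 and the definition would have to change instead, with a reason given. Either way, one rule should be stated in advance.
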